6.	Stu	udy objectives1	1
6	.1.	Primary objective1	1
6	.2.	Secondary objective1	1
6	.3.	Primary endpoint12	2
6	.4.	Secondary endpoint	2
7.	Stu	udy population12	2
7.	.1.	Inclusion criteria	2
7.	.2.	Exclusion criteria13	3
8.	Stu	udy design13	3
9.	Stu	udy procedures	3
9	.1.	Case Identification	3
9	.2.	Data collection	4
9	.3.	Facilitation of data returns1	5
9	.4.	Follow up1	5
9	.5.	End of study definition	3
10.	:	Statistical considerations	3

10.1	1.	Sample size	16
10.2	2.	Method of analysis	16
10.3	3.	Criteria for progression	17
10.4	4.	RC&Plasma metrics	20
11.	Eth	nics	20
11.1	1.	Annual Safety Reporting	21
12.	Pul	blic involvement	21
13.	Da	ta handling and record keeping	22
13.1	1.	Data management	22
13.2	2.	Source Data	22
13.3	3.	Confidentiality	23
1	3.3.′	1. Participant confidentiality	23
13.4	4.	Record retention and archiving	23
14.	Sat	fety reporting	23
15.	Мо	nitoring and auditing	23
16.	Stu	udy committees	23
17.	Fin	ance and funding	24
18.	Ins	urance and indemnity	24
19.	Dis	ssemination of research findings	24
20.	References		

2. Glossary

CI	Chief Investigator
CRF	Case Report Form
FFP	Fresh frozen plasma
JRMO	Joint Research Management Office
NHSBT	NHS Blood and Transplant
NHS REC	National Health Service Research Ethics Committee
NHS R&D	National Health Service Research & Development
RBC	Red blood cells
RC&Plasma	Red cells and plasma
RLH	Royal London Hospital

3. Signature page

Chief Investigator Agreement

The study, as detailed within this Research Protocol, will be conducted in accordance with the principles of Good Clinical Practice, the UK Policy Framework for Health and Social Care Research, and the Declaration of Helsinki and any other applicable regulations. I agree to take responsibility for the statistical analysis and oversight of this study.

Chief Investigator Name: [name]

Signature:

[name]

Date:

11.04.2018

4. Summary and synopsis

Short title	Red blood cell and plasma transfusion in the pre-hospital setting			
Methodology	Observational Cohort study collecting anonymised data only			
	Primary objective Assess the feasibility of delivering RC&Plasma components into clinical practice.			
Objectives / aims	Secondary objectives Compare the impact of RC&Plasma transfusion with red blood cell (RBC) transfusion (retrospective data) and RBC and fresh frozen plasma (FFP) transfusion (prospective data from Newcastle and Oxford hospital) on: resuscitative effect (base excess, lactate), coagulation parameters, overall transfusion requirement, haemolysis, days in hospital and mortality, in trauma bleeding patients.			
Number of participants	140 in the RC&Plasma arm 200 in the RBC arm (retrospective) 150 in the RBC and FFP arm			
Inclusion and exclusion criteria	 Inclusion criteria All trauma patients requiring pre-hospital major haemorrhage protocol activation by the pre-hospital team because of haemorrhagic shock and for whom clinician has transfused a RC&Plasma component (in London), or RBC and FFP by either the Great North or Thames Valley Air Ambulance. Patients who have received at least one RBC unit in the pre-hospital setting because of trauma haemorrhage between March 2015 and April 2018 (retrospective cases) 			
Study duration	2 years			

5. Introduction

Uncontrolled bleeding due to trauma is associated with significant morbidity and mortality, and substantial costs to NHS. Early administration of fresh-frozen-plasma (FFP) and platelets in a high (near 1:1:1) ratio with red blood cells (RBC) reduces mortality, and this has now become standard of care for trauma patients who are bleeding. However, the logistics of delivering FFP together with RBC in the pre-hospital setting could delay transfer to hospitals (which could be detrimental), and also place additional demands on the clinical team. Availability of a component that contains red cells and plasma (RC&Plasma) in a single bag could overcome these challenges. Such component is available in the UK: however, it is not used routinely. Furthermore, the efficacy and safety relative to other transfusion strategies have not been investigated in randomised controlled trials.

The Royal London Hospital Major Trauma Service and the Helicopter Emergency Medical Service, have made a clinical decision to change standard treatment for the management of trauma patients who are bleeding in the pre-hospital setting, from the transfusion of RBC to the transfusion of RC&Plasma for 24 months.

The overall objectives of this project are to:

- a. assess if it's feasible to deliver RC&Plasma component to patients who are bleeding in the pre-hospital setting, so that we can lay the groundwork for a future trial that will compare the efficacy and safety of different transfusion strategies
- b. evaluate the impact of the RC&Plasma transfusion in trauma bleeding patients in the pre-hospital setting on: transfusion requirements, rate of haemolysis, resuscitative effect, days in hospital, rate of thrombosis, and mortality by comparing these with RBC transfusion only (using retrospective data) and RBC and FFP transfusion (prospective data from Newcastle and Oxford hospitals);

5.1. Background

5.1.1. Transfusion management of trauma bleeding

Uncontrolled bleeding accounts for 40% of all trauma deaths with the costs of management being around £150 million for the NHS (Campbell, *et al* 2015). A timely and organised approach to transfusion in the management of bleeding is crucial to improving clinical outcomes. In 2015, a randomised controlled study (PROPPR) showed that early administration of fresh frozen plasma (FFP) and platelets in a 1:1:1 ratio with red blood cells (RBC) reduces death from exsanguination at 24 hours compared with a 1:1:2 ratio (Holcomb, *et al* 2015), and these results informed national guidelines on the management of major bleeding recommending that FFP be given empirically and early in the initial resuscitation process in 1:1 ratio with RBC ([NG39] 2016, Hunt, *et al* 2015). The precise role of platelets is unclear, with recent guidelines being unable to make any strong recommendations for platelet transfusions. There is some evidence that platelet transfusions may be more effective when given very early in the clinical course of bleeding (Holcomb, *et al* 2015).

In March 2012 for the first time in the UK, the Royal London Hospital allowed the pre-hospital team to transfuse RBC on-scene to trauma patients who were bleeding: this has contributed to reduction in the pre-hospital mortality from 42% in 2009 to 27% in 2015 (p <0.01). However, in the pre-hospital setting the logistics of delivering FFP in addition to RBC could be quite challenging as this would: a) necessitate additional weight for the pre-hospital personnel approaching the scene of the accident; b) increase the complexity of resuscitating patients because several bags (blood and fluid) would need to be administered to a patient who may not have enough intravenous access, and clinical team are occupied doing other important tasks; and b) delay the transfer of patients to hospital because clinical team would attempt to transfuse both RBC and FFP at the scene, which could be potentially detrimental to outcome (Meyer, et al 2017). While some trauma centres like Newcastle and Oxford have decided to transfuse RBC and FFP in the pre-hospital setting, clinicians realise that a single whole blood (WB) product that contains everything in one bag (RBC, FFP and Platelets) would be ideal, but this is not yet possible in the UK due to current manufacturing procedures removing platelets from WB donations. Another product that contains RBC and FFP in one bag (RC&Plasma thereafter) is available in the UK, and has been used in the past, but it is not currently in routine use. Moreover, studies comparing its efficacy and safety, against standard blood components have not been conducted.

5.1.2. Blood components

Whole blood component (WB) was used routinely by the military between 1940 to 1960 to treat soldiers during World War II, Korean War, Vietnam War, and also in the most recent conflicts in Bosnia, Kosovo, and Iraq. This component was transfused to patients within 24 hours of it being donated (known as fresh WB). By 1965 the use of fresh WB reduced significantly due to the introduction of blood components (i.e. RBC, FFP, Platelet), which made targeted replacement therapy of missing clotting factors possible, and in so doing it minimized the potential risks and side effects of receiving unneeded blood components. Further, the longer shelf-lives of blood components, compared with fresh WB, made the logistics of supply and demand more manageable for the blood manufacturing units. All these contributed to the rapid disappearance of (fresh) WB.

In the UK all blood components have to undergo removal of leucocytes (called leucocyte - depletion) as a safety measure to reduce the risk of variant-CJD transmission. However, the filters that are used will also remove platelets in addition to leukocytes, thus the remaining component will contain only red cell and plasma (or RC&Plasma thereafter). Since the introduction of the leucocyte depletion process in 1999, NHSBT has issued approximately 3,000 units of RC&Plasma components. This component is not currently routinely issued to hospitals, albeit around 1,000 units per year of a similar product (containing a lower plasma volume of ~50mL) has been issued by NHSBT to support intrauterine and neonatal transfusion since 1999.

5.2. Rationale

In the recent years there has been a huge interest in revisiting the transfusion of RC&Plasma component in bleeding patients, particularly for those presenting with trauma in the prehospital setting, and where support with plasma transfusion in addition to red cells, could be quite challenging. However, studies evaluating its efficacy and safety against standard care are non-existent, and prior to performing such studies, we need to first establish the feasibility of making this component available to pre-hospital teams, considering that it has a shorter

shelf-life than RBC (14 versus 35 days), and that its production could increase hospital blood wastage, and also impact the manufacturing of other blood components needed for other settings.

A clinical decision has been made by the Royal London Hospital (RLH) Major Trauma Service and the Helicopter Emergency Medical Service, to change standard treatment for the management of trauma patients who are bleeding in the pre-hospital setting, from the transfusion of RBC to transfusion of RC&Plasma component, for a period of 2 years beginning June 2018. Some medical services like Great North Air Ambulance and Thames Valley Air Ambulance have decided to transfuse RBC and FFP in the pre-hospital setting.

The overall aim of this project is to assess if it's feasible to deliver RC&Plasma component (and eventually whole blood by extension) to patients who are bleeding in the pre-hospital setting, so as to lay the groundwork for a future trial that will compare the efficacy and safety of different transfusion strategies.

5.3. Risks / benefits

This is an observational study that will assess if it is operationally possible to deliver RC&Plasma component to patients who are bleeding in the pre-hospital setting, with the view to performing a future randomised control trial that will compare different transfusion strategies. RC&Plasma component has been used in the past in the UK without any safety concerns, and from June 2018 the RLH Major Trauma Service and the Helicopter Emergency Medical Service have made a clinical decision to transfuse this component (instead of RBC) to trauma patients who are bleeding in the pre-hospital setting. The main benefit of the study will be to inform the future trial, which in turn will improve transfusion treatment of bleeding patients.

6. Study objectives

6.1. Primary objective

- Assess the feasibility of delivering RC&Plasma component into clinical practice and understand the operational and financial impact (for both NHSBT and NHS hospitals) of implementing the RC&Plasma component into clinical practice in the future.
- Determine RC&Plasma wastage in hospital

6.2. Secondary objective

Compare the impact of RC&Plasma transfusion with RBC transfusion (retrospective data between March 2015 to April 2018) and RBC and FFP transfusion (prospective data from Newcastle and Oxford hospital) on: resuscitative effect (base excess, lactate), coagulation parameters, overall transfusion requirement, haemolysis, days in hospital and mortality, in trauma bleeding patients.

6.3. Primary endpoint

- 1. Percentage of 'On-time-in-Full' (OTIF) delivery from NHSBT to RLH, defined as:
- occasions when product is delivered to agreed / requested schedule, and
- occasions when product delivered to specification,

Therefore, OTIF will be Percentage of occasions per annum where component was delivered as specified and as scheduled or requested.

2. Wastage of RC&Plasma component at Royal London Hospital per anum.

Data on both outcomes will be collected monthly and aggregated at study end.

The results of this study will be used to build a model that can predict wastage using userspecific parameters such as: demand for RC&Plasma in pre-hospital and hospital trauma settings and day-to-day deliverability of RC&Plasma, with a view to determining the optimum pattern of supply that will adequately meet demand and yet result in minimal wastage for individual hospitals.

6.4. Secondary endpoint

To evaluate the clinical impact of RC&Plasma transfusion versus RBC transfusion and RBC and FFP transfusion, the following clinical data will be collected:

- Changes in base deficit and prothrombin time from scene to emergency department
- Transfusion wastage (red blood cells, fresh frozen plasma, platelets, cryoprecipitate) at 24-hours post injury
- Transfusion requirement at 24 hours and up to hospital discharge or 28 days, or death whichever occur first
- Total hospital length of stay
- Survival analysis up to 24-hours and 28 days post injury

Other factors that will be monitored include: *NHSBT*

- Wastage (units per month)
- Substitutions (units per month)
- Impact on supply of other blood components
- Impact on other processes
- Additional administration resources and time required to provide RC&Plasma

Hospital

- Additional administration support and time required to support clinical team
- % of RC&Plasma used in the pre-hospital setting
- % of RC&Plasma used in emergency department

7. Study population

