10.1. Sample size

Primary Outcome:

The primary outcome is the percentage of occasions per annum where component was delivered as specified and as scheduled or requested from hospital. It has been agreed between RLH and NHSBT that RC&Plasma component will not be delivered during bank holidays, and in these days 'On-time-in-full' calculation will be excluded. The current NHSBT OTIF standard is 98%. The study will be declared feasible if OTIF is achieved in at least 97.3% (95%CI: 95.7% - 98.4%).

The criteria for progression on wastage level is given under section 13.3 below.

Secondary Outcomes:

Since March 2012 when the Royal London team started carrying RBC on board, on average 70 patients per year have been transfused an average of 2 units of RBC in the pre-hospital setting. We therefore project that around 140 patients will be transfused with a RC&Plasma component during the study period (24 months). Based on The London ambulance data analysis of patients, approximately 70% of trauma patients who receive a RBC transfusion arrive in emergency department with a Base Deficit >6 mEq/L. Assuming a retrospective cohort of approximately 160 patients and at least 60 patients in the RC&Plasma arm, the study will have 80% probability (power) at 5% level of significance of detecting an absolute 20% reduction in the proportion of patients arriving in emergency department with a Base Deficit >6 mEq/L in the RC&Plasma group. The required sample size is attainable even after postulating a loss-rate of 25% (e.g. blood samples not being taken due to patients dying etc.).

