10.2. Method of analysis

Statistical analyses will be performed using STATA (StataCorp, USA). Categorical variables will be tabulated as frequencies and percentages and compared using Fisher's exact tests; continuous variables will be summarised as means [standard deviation] or medians [interquartile range] and compared using t-tests or non-parametric equivalents. All tests will be two-sided at the 5% level of significance. Multivariable regression models will be used to examine the association between treatment groups (RC&Plasma versus RBC-only transfusions) and various clinical outcomes, controlling for potential confounders (including but not limited to: type and location of injury; age; other co-morbidities) as appropriate.

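### The scene-to-ED change endpoints have no stated adjusted analysis against RBC and FFP, no named covariate for shock at scene, and no power statement of their own

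*Protocol*

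**What the plan says.** Protocol section 6.4 gives, among the clinical data for RC&Plasma against RBC and against RBC and FFP, "Changes in base deficit and prothrombin time from scene to emergency department". Section 6.2 names the same two comparators.

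Section 10.2 sets the methods in general terms. For unadjusted comparisons, "continuous variables will be summarised as means [standard deviation] or medians [interquartile range] and compared using t-tests or non-parametric equivalents". For adjusted ones, "Multivariable regression models will be used to examine the association between treatment groups (RC&Plasma versus RBC-only transfusions) and various clinical outcomes". The covariates for these models are set by a clause that leaves the list open: "controlling for potential confounders (including but not limited to: type and location of injury; age; other co-morbidities) as appropriate". On significance testing, the section adds: "All tests will be two-sided at the 5% level of significance".

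Section 10.1 contains the only power statement for a clinical outcome. It starts from "approximately 70% of trauma patients who receive a RBC transfusion arrive in emergency department with a Base Deficit >6 mEq/L" and claims 80% power, with about 160 RBC and at least 60 RC&Plasma patients, for an "absolute 20% reduction in the proportion of patients arriving in emergency department with a Base Deficit >6 mEq/L in the RC&Plasma group".

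Table 1 in section 9.2 collects laboratory results from scene to ED. The bracketed examples are haemoglobin, platelets, coagulation tests and lactate.

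**The concern.** Three things do not fit together.

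- **A comparator without an adjusted analysis.** The objective and the endpoint list give two comparators, but the regression sentence names one. For RBC and FFP, the only method on the page is a two-sample test between patients treated by different services.
- **No named measure of starting severity.** The covariates named are injury type and location, age and co-morbidities. None measures shock at scene, although a change endpoint already needs the scene value.
- **Power for an unlisted outcome.** The powered quantity is a binary ED level. The listed endpoint is a continuous change. The 80% therefore applies to no endpoint in 6.4.

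What is at stake is how the clinical comparisons are read when they are used to prepare the future trial. An unadjusted difference in change can reflect where the cohorts started, and a reader may attach the 80% power to the wrong endpoint.

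**Working it through.** **1. Which analysis covers which contrast (section 10.2).**

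| Contrast | Two-sample test | Regression | Scene value |
|---|---|---|---|
| RC&Plasma v RBC | stated | stated, open covariate list | not named, not excluded |
| RC&Plasma v RBC and FFP | stated | not stated | no covariate list applies |

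**2. Are scene differences foreseeable?** Section 7.1 requires major haemorrhage protocol activation and haemorrhagic shock for the RC&Plasma cohort. The retrospective RBC cohort needs only RBC transfusion in the stated period, and the synopsis adds no shock criterion for it. For RBC and FFP the text is less clear: 7.1 lists haemorrhage but not shock, while the synopsis applies shock to both prospective cohorts. There, the ground for expecting a difference is mainly that another service treated the patients.

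**3. The plan's own power figure.** Inputs from 10.1: 70% v 50%, 160 v 60, two-sided 5%.
- Pooled proportion = (160×0.70 + 60×0.50)/220 = 0.6455.
- Null SE = √[0.6455×0.3545×(1/160 + 1/60)] = 0.0724.
- Alternative SE = √(0.21/160 + 0.25/60) = 0.0740.
- z = (0.20 − 1.96×0.0724)/0.0740 = 0.784, so power = 78.4%.

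Exact power for Fisher's test, which 10.2 names, is 75.9%. The stated 80% is reproduced to within 2 points by the normal approximation and is not in dispute. The calculation uses no scene value and no change score, so it does not transfer to the listed endpoint.

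**4. Precision of the two contrasts.** The protocol gives no SD and no scene-to-ED correlation r, so r is assumed, with equal variances at scene and ED. In units of the ED variance, change has 2(1−r), the scene-adjusted contrast has 1−r², and their ratio is (1+r)/2.

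| r (assumed) | Change | Adjusted | Ratio | Gap between estimates per 1 SD scene difference | Ratio if scene means differ by 1 SD |
|---|---|---|---|---|---|
| 0.3 | 1.40 | 0.91 | 0.65 | 0.7 SD | 0.78 |
| 0.5 | 1.00 | 0.75 | 0.75 | 0.5 SD | 0.90 |
| 0.7 | 0.60 | 0.51 | 0.85 | 0.3 SD | 1.02 |
| 0.9 | 0.20 | 0.19 | 0.95 | 0.1 SD | 1.14 |

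The fourth column gives the variance reduction of 35% to 5%. It holds when the scene means are similar. If they differ by 1 SD (an illustration, not a documented figure), the adjusted variance is multiplied by 1 + (160×60)/220² = 1.198 at the 10.1 group sizes. The last column shows the result: the gain shrinks and is gone by r = 0.7.

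**5. What the gap means.** With equal variances, the change contrast is D(ED) − D(scene) and the adjusted contrast is D(ED) − r×D(scene), where D is the difference between groups. They differ by (1−r)×D(scene). This is a disagreement between two estimators. It becomes the bias of one of them only once an assumption about the untreated course is made.

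**The case against.** The strongest reply has five parts.

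- **Regression is planned and its covariate list is open.** This stands. A reader might infer that the protocol ignores the scene value. It does not: for RC&Plasma against RBC the value is unnamed, not excluded, and the wording "compared using t-tests or non-parametric equivalents" is generic and not tied to the change endpoint. The exact covariate set also commonly belongs in the SAP. The reply does not reach the RBC and FFP contrast, because the protocol itself limits the regression to the other comparator.
- **Adjustment is not clearly the right estimator here.** This also stands. If two cohorts differ stably by 1 SD at both scene and ED with no treatment effect, the change contrast is 0 and the adjusted one is 1−r, that is 0.7 to 0.3 SD for r of 0.3 to 0.7. A reader might infer that the change score is biased by that amount, but the documents do not support either assumption over the other.
- **The power statement is untouched.** Correct. A reader might also infer that the binary outcome should give way to a continuous one. Under a normal model, 70% v 50% is a shift of 0.524 SD, with 93% power on the continuous ED value against 76% by Fisher's test. That concerns the ED level, not the change, and rests on normality. It is no ground for demoting the one outcome the protocol powered, which needs only an ED sample.
- **The powered outcome falls under the objective.** Section 6.2 includes base excess, and the ED value is one half of the change. So the data are there, but 6.4 still does not list the outcome.
- **Nothing decisive depends on it.** Neither the primary endpoints in 6.3 nor the progression criteria in 10.3 use base deficit or prothrombin time. This stands and sets the weight of the point.

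**Conclusion.** The point holds as a minor one, in three parts that can be read from the protocol alone: no adjusted analysis is stated for RC&Plasma against RBC and FFP; no named covariate measures shock at scene, although the entry criteria make a difference foreseeable, most clearly against the retrospective RBC cohort; and the stated power applies to an outcome that 6.4 does not list.

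The size cannot be fixed from the document. With r assumed between 0.3 and 0.9, equal variances and similar scene means, adjustment lowers the variance by about 35% to 5%, and by less or not at all if the scene means differ widely. The main reason to name the scene value is therefore to show how far the result depends on where the cohorts started. Neither the adjusted nor the unadjusted contrast removes all confounding between non-randomised groups.

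**What to change.** **Section 10.2.** Extend the regression sentence to both comparators, RBC and RBC and FFP. For base deficit and prothrombin time, name the scene value as a covariate next to the confounders already given. Report the unadjusted change contrast alongside, and say that the two rest on different assumptions.

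**Section 6.4.** List ED base deficit above 6 mEq/L as the powered secondary outcome, so that the power statement in 10.1 has an endpoint to refer to. Keep the change endpoints.

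**Table 1.** Confirm that the CRF captures base deficit at scene and in ED, since the bracketed laboratory list does not name it. State whether the scene sample precedes the transfusion, because a value taken after it is not a clean baseline.

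**Cost.** Analysis wording, plus possibly one CRF item. Patients without a scene value drop out of the adjusted model, as they already do for change. The 25% loss rate in 10.1 was set for an outcome that needs only an ED sample, so the number with both values may be smaller and should be reported for each cohort.
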